### ***Medications***

***STIOLTOTTM RESPIMAT®***: Two actuations of STIOLTOTTM RESPIMAT®, taken once daily, provides 6.2 micrograms of tiotropium bromide monohydrate and 5.5 micrograms olodaterol hydrochloride, which is equivalent to 5.0 micrograms of tiotropium and 5.0 micrograms of olodaterol.

Tiotropium bromide is a non-chiral, long-acting, inhaled anticholinergic bronchodilator initially developed for the long-term, once-daily, maintenance treatment of bronchospasm and dyspnea associated with chronic obstructive pulmonary disease (COPD), including chronic bronchitis and emphysema. It has had FDA approval for use in COPD for over 10 years and is used in COPD more than any other bronchodilator medication.

Olodaterol hydrochloride is a long-acting beta2-adrenergic agonist bronchodilator indicated for the long-term, once-daily maintenance bronchodilator treatment of airflow obstruction in patients with chronic obstructive pulmonary disease (COPD), including chronic bronchitis and/or emphysema. It has had FDA approval for use in COPD for about 2 years.

PROTOCOL TITLE: A randomized, crossover, placebo controlled, double-blind phase IV trial of the effect of on STIOLTO™ RESPIMAT® on central and peripheral components of fatigue during exercise in chronic obstructive pulmonary disease  
Revised: November 13, 2015

The drug product, STIOLTO™ RESPIMAT® is composed of a sterile aqueous solution of tiotropium bromide and olodaterol hydrochloride filled into a 4.5 mL plastic container crimped into an aluminum cylinder (Stiolto™ cartridge) for use with the Stiolto™ Respimat® inhaler.

The drug package insert is attached to this application.

*Placebo Respimat®*: The placebo Respimat® inhaler will be prepared by the manufacturer and contains no active therapeutic agent.

*Albuterol*: Albuterol is an FDA approved medication for pulmonary function testing. It may be used in this study as a short-acting medication during washout periods. The drug package insert is attached to this application.

*Combivent*: Combivent contains ipratropium bromide and albuterol. Ipratropium bromide is a marketed drug approved for use in the United States. It is a bronchodilator for maintenance treatment of bronchospasm (tightening of the airways) associated with COPD, including chronic bronchitis and emphysema. It may be used in this study as a maintenance therapy during washout periods. The drug package insert is attached to this application.

*Inhaled corticosteroids (ICS)*: Some COPD patients take combination therapies that contain an inhaled corticosteroid and a long-acting bronchodilator in one dose. In these cases, patients will be transitioned to inhaled corticosteroid monotherapy for the duration of the study. ICS monotherapy may be used in this study as a maintenance therapy. The drug package insert is attached to this application.

### ***Procedures***

An assessment schedule for the procedures in the study is shown in Table 1.

*Pulmonary function*: Visit 1 will include spirometry, lung volume by body plethysmography, and single-breath carbon monoxide diffusing capacity tests. Each will be made according to ATS/ERS guidelines, at least 10 min after 200 µg of albuterol (Millar et al., 2005). Visits 2-5 will include spirometry prior to each exercise test.

*Resting ECG*: Visit 1 will include a resting 12 lead ECG to determine a normal electrocardiogram prior to any exercise testing.

*Medical history and questionnaires*: During visit 1 a medical history will be collected, including respiratory and heart history, smoking history, and medication history. Patients will also complete the St. George's Respiratory

PROTOCOL TITLE: A randomized, crossover, placebo controlled, double-blind phase IV trial of the effect of on STIOLTOT™ RESPIMAT® on central and peripheral components of fatigue during exercise in chronic obstructive pulmonary disease  
 Revised: November 13, 2015

Questionnaire (SGRQ) and the COPD Assessment Tool (CAT) to assess COPD symptoms.

**Table 1.** Assessment Schedule

Study phase	Consent	Screening PFT	Baseline & Randomization	Fatigue test 1	Fatigue test 2	Isotime test
Visit number	-	1	2	3	4	5
Study days	up to -17	-14	0	7	28	49
Inclusion / Exclusion criteria	x	x				
Relevant History, Physical Exam		x				
Height & Weight		x	x	x	x	x
Spirometry		x	x	x	x	x
Lung Volumes		x	x	x	x	x
DL CO		x				
Resting ECG		x				
NIRS Oxidative Capacity Test		x				
CPET & ECG (Incremental)			x			
CPET & ECG (CWR)			x	x	x	x
EMG (Accessory & Leg muscles)			x	x	x	x
Isokinetic Test – Baseline Calibration			x	x	x	x
Isokinetic Test - Fatigue			x	x	x	x
Exercise Leg NIRS			x	x	x	x
Ventilation & Gas Exchange			x	x	x	x
Dynamic Hyperinflation			x	x	x	x
Comments				As required		

*Non-invasive assessment of oxidative capacity by NIRS:* Visit 1 will include measurement of quadriceps muscle oxygenation by near-infrared spectroscopy (NIRS; Hamamatsu Photonics KK) during a supine protocol using intermittent venous and arterial occlusion (Ryan et al., 2012). The FDA deems use of NIRS in humans as a ‘non-significant risk’. The recovery dynamics of muscle O2 consumption after brief, light muscle contractions is directly determined by mitochondrial oxidative capacity in vivo (McCully et al., 1993). We will use this for non-invasive assessment of vastus lateralis oxidative capacity by NIRS, together with an assessment of muscle vasoreactivity (Ryan et al., 2012). Briefly, the protocol consists of five key phases: 1) resting muscle oxygenation (2 minutes); 2) Ten intermittent venous occlusions (~50 mmHg cuff pressure, for 20 seconds each) to determine resting muscle blood flow; 3) Three arterial occlusions (~250 mmHg cuff pressure, for 30 seconds each) to measure resting muscle oxygen consumption; 4) a sustained arterial occlusion (maximum 5 minutes) and recovery for physiologic calibration and to characterize vasoreactivity during cuff release; 5) Ten seconds of low-intensity rhythmic knee-extension followed immediately by high-frequency intermittent arterial occlusions (~250 mmHg cuff pressure) to estimate recovery O2 consumption dynamics for ~5 minutes; 6) a repeat of item 5 to improve signal-to-noise. The assessment takes approximately 30-35 min in total.

PROTOCOL TITLE: A randomized, crossover, placebo controlled, double-blind phase IV trial of the effect of on STIOLTOT™ RESPIMAT® on central and peripheral components of fatigue during exercise in chronic obstructive pulmonary disease  
Revised: November 13, 2015

*Incremental exercise test:* All patients will perform a ramp-incremental cycle exercise on an electromagnetically-braked cycle ergometer (Excalibur Sport PFM, Lode NL) to the limit of tolerance after an overnight washout of short-acting bronchodilator (visit 2). Patients will breathe through a mouthpiece with nose clip in place for measurement of respired gases and volumes for breath-by-breath gas exchange and ventilatory measurements (Vmax Spectra, CareFusion USA). Tests will be administered with 3 minutes of rest and at least 3 minutes of unloaded cycling (until a steady-state is achieved), followed by an increase in power output at 5 W/min (for patients with  $FEV_1 \leq 1$  L) or 10 W/min (for patients with  $FEV_1 > 1$  L) and continued to the limit of tolerance. The limit of tolerance will be determined as the point at which the patient experiences intolerable dyspnea or is unable to maintain pedaling rate above 50 rpm despite verbal encouragement. At the limit of tolerance and every 1 minute during recovery an isokinetic power test will be performed (described below). At specified times during the exercise test, inspiratory capacity (IC) measurements will be made using a maximum inhalation. These will be made at rest, every 2 min during exercise, at end-exercise, and every 1 minute during recovery

*Constant work rate (CWR) exercise tests:* From an unloaded pedaling baseline (~3 min), the power output will be abruptly increased to approximately 75% WRpeak (this is the peak work rate achieved during the incremental exercise test). The specific work rate chosen will be chosen to elicit intolerance in ~6 min in the placebo condition (van der Vaart et al., 2013). The patient will be instructed and encouraged to maintain the power output for as long as they can manage (except in the isotime test, as noted below). Patients will breathe through a mouthpiece with nose clip in place for measurement of respired gases and volumes for breath-by-breath gas exchange and ventilatory measurements (Vmax Spectra, CareFusion USA). A familiarization CWR test will be performed at visit 2, at least 1 hour after the incremental test. At specified times during the exercise test, inspiratory capacity (IC) measurements will be made using a maximum inhalation. These will be made at rest, every 2 min during exercise, at end-exercise, and every 1 minute during recovery

The constant power test will be repeated on at least 4 occasions. The initial constant power test will be made at least 2 hours after the incremental test and will be used to identify the ~6 min endurance time in untreated conditions (visit 2). If the endurance time is not ~6 min (in the range 4-10 minutes), then an additional visit (visit 2a) will be made to identify required power output. After this, two constant power tests will be performed to intolerance with either STIOLTOT™ RESPIMAT® or placebo (visits 3 and 4). An additional, third constant power test will be performed using the treatment condition that resulted in the longest endurance time (visit 5). For this test the isokinetic measurements will be made at a time when the shorter of the two treatment tests ended,

PROTOCOL TITLE: A randomized, crossover, placebo controlled, double-blind phase IV trial of the effect of on STIOLTOT™ RESPIMAT® on central and peripheral components of fatigue during exercise in chronic obstructive pulmonary disease  
Revised: November 13, 2015

providing isotime assessment. The condition (active drug vs placebo) of visits 3-5 will remain blinded to the participants and the experimenters until the end of the study. At the limit of tolerance and every 1 minute during recovery an isokinetic power test will be performed (described below).

*Isokinetic power tests (baseline and fatigue):* Patients will be familiarized with the maximal isokinetic cycling task at visit 2. Initially patients will be oriented to the cycle ergometer and optimal seat height will be determined. Following this, isokinetic ergometry tests will be performed at baseline, at the limit of tolerance, and in recovery during visits 2 (incremental exercise) and 3-5 (constant work rate tests).

At baseline subjects will cycle at a comfortable cadence with zero load for ~3 min, after which they will be asked to perform 5 pedal strokes (~4 seconds) isokinetic cycling at each of ~25%, ~50%, ~75% and 100% maximal effort. The strain of the task is minimal and only a few seconds (~30 s) recovery is necessary between each effort, but subjects will be given as long as they feel is necessary to recover. During these efforts the flywheel braking of the cycle ergometer is controlled to result in predetermined velocities equating to a constant pedal cadence of 70 rpm. Patients will complete this test twice at baseline (unfatigued condition) prior to each exercise test to ensure reproducibility. If the two repeats do not cohere to within 10%, then the procedure is repeated a third time following a short (~10 min) rest. The patient will then be given 30 minutes to recover before the incremental or CWR exercise test is performed.

During each exercise test, isokinetic fatigue tests will be made at the point of limitation (or at isotime) and during recovery. For this the cycle ergometer will be switched to isokinetic mode and five pedal strokes will be completed at maximal effort (~4 seconds) to determine PF, AF and MF. In order to track fatigue during recovery, 5-pedal-stroke maximal isokinetic efforts will also be made every minute during recovery until the fatigue has recovered to 90% of the baseline value (up to a maximum of 6 minutes; 3-4 minutes is typical).

*Exercise NIRS:* Tissue oxygenation during exercise will be assessed by NIRS (as described above in *Non-invasive assessment of oxidative capacity by NIRS*). NIRS probes will be attached by adhesive tape to the skin of the quadriceps (for muscle oxygenation) and the forehead (for cerebral oxygenation), and a bandage will be placed over the probe to help ensure its stability during exercise.

### ***Measurements***

*Ventilation, gas exchange, heart rate, and perceived exertion during exercise:*

During incremental and CWR exercise, patients will breathe through a mouthpiece for breath-by-breath pulmonary gas exchange and ventilation measurement (Vmax Encore, CareFusion USA). Heart rate, arterial oxygen

PROTOCOL TITLE: A randomized, crossover, placebo controlled, double-blind phase IV trial of the effect of on STIOLTOT™ RESPIMAT® on central and peripheral components of fatigue during exercise in chronic obstructive pulmonary disease

Revised: November 13, 2015

saturation, and transcutaneous CO2 partial pressure will also be measured.

[figure not shown]
Patients will be asked to rate their perceived exertion (“rate your leg fatigue” and “rate your difficulty of breathing”) every 2 minutes during exercise and recovery. All methods are well established in our lab. From these measurements the following variables will be determined in the incremental test: Peak oxygen uptake, lactate threshold (LT), ventilatory equivalent for CO2 at LT as an index of ventilatory efficiency, peak ventilation (also expressed relative to maximum voluntary ventilation calculated from pulmonary function tests).

*Tissue oxygenation:* Tissue oxygenation dynamics [(oxygenated hemoglobin and myoglobin) / (total heme-chromophor concentration)] will be measured in the quadriceps using spatially-resolved near-infrared spectroscopy (NIRO200, Hamamatsu; as previously described in our laboratories; Bowen et al., 2012). Kinetic modeling of deoxygenation response dynamics will be made by non-linear least squares fitting procedures to determine the association between tissue oxygenation and fatigue characteristics.

*Dynamic hyperinflation (DH):* DH will be evaluated from inspiratory capacity (IC) measurements at rest, every 2 min during exercise, and at end-exercise and during recovery (Somfay et al., 2001) immediately prior to the AF and MF measurement. This reproducible method allows dynamic changes in the operational lung volume to be determined.

*Isokinetic power and leg muscle activity:* Wireless surface electromyography (EMG) sensors (Trigno, Delsys) are fitted using adhesive patch on the quadriceps, hamstrings, and gastrocnemius. Pedal torque is measured at the crank every 2° of rotation and mean isokinetic power is determined over each complete revolution. Using these measurements a relationship between the average root mean square EMG activity (RMS EMG) and power output can be generated (Coelho et al., 2015). The baseline (unfatigued) relationship between RMS EMG and power becomes the reference value. The fatigue point is then placed in the context of the reference value (see Fig 2). Performance fatigue (PF) is the decline in power output at maximal effort between baseline and the measurement during fatigue. The activation fatigue (AF) is the power-equivalent of the reduction in RMS EMG activity between the maximal effort at baseline and during fatigue. The muscle fatigue (MF) is the difference in power output between that expected (at baseline) at the achieved RMS EMG and the measured power (see Fig 2).

PROTOCOL TITLE: A randomized, crossover, placebo controlled, double-blind phase IV trial of the effect of on STIOLTOTM RESPIMAT® on central and peripheral components of fatigue during exercise in chronic obstructive pulmonary disease  
Revised: November 13, 2015

**Figure 2.** Relationship between isokinetic power and muscle activity (EMG). The baseline (unfatigued) relationship is shown in grey and dashed-line. At the limit of tolerance in incremental exercise fatigue is assessed from a single 5-pedal maximal effort (open circle). Recovery of fatigue is shown at 1 (horizontal bar), 2 (vertical bar), and 3 (plus sign) minutes after intolerance. A graphical depiction of the method to qualify performance fatigue (PF), activation fatigue (AF), and muscle fatigue (MF) is shown in red. Note that in this example, performance fatigue at end-exercise is approximately 30% activation fatigue and 70% muscle fatigue. Recovery of muscle fatigue is essentially complete 3 minutes after end-exercise.

*Accessory muscle activation:* Wireless electrodes will be placed over the accessory muscle of breathing e.g. sternocleidomastoid, scalene muscles, to record electromyographic activity (Trigno, Delsys).

#### **h) Data and Specimen Banking\***

Data will be stored for at least 3 years required by the USDHSS, in password-protected PCs and secure filing cabinets in the CDCRC Building. Data will be stored indefinitely.

In order to minimize the risk of inappropriate use of medical information, no data will be labeled in a way that they can be readily identified to an individual. Participants will de-identified using a number code system and the key will be kept in a separate locked cabinet in the PI's office or records room.

PROTOCOL TITLE: A randomized, crossover, placebo controlled, double-blind phase IV trial of the effect of on STIOLTO™ RESPIMAT® on central and peripheral components of fatigue during exercise in chronic obstructive pulmonary disease  
Revised: November 13, 2015

Electronic documents will be stored on password-protected PCs in the CDCRC Building. Source documents will be stored in secure filing cabinets in a locked records room in the CDCRC Building. The PI and co-investigators will have access to the data.

Protected health information linking the data and samples to subject identity will be kept for 25 years after the consent is executed.

The LA BioMed training requirement (Study Volunteer Protection, HIPAA Compliance, and Good Clinical Practices) will be satisfied before any investigator handles data.

**i) Data Management \***

***Power calculation***

Formal power analyses for these measurements are difficult to compose due to the novelty of the approach. Unpublished work from our lab (LA BioMed protocol 30044-01) were able to detect an average 22% (PF = 24 Watt;  $p = 0.02$ ) decrease in paired measures of isokinetic performance fatigue at isotime in 13 COPD patients with a inhaled oxygen as the intervention. This reduction in fatigue (increase in power) was due to significant reduction in activation fatigue (AF = 33 Watt reduction;  $p=0.03$ ) and a non-significant increase in muscle fatigue (MF = 9 W increase;  $p=0.26$ ). However, the expected difference in PF and AF following bronchodilator therapy are less than for inhaled oxygen. Saey et al., (2003) found a significant 10% difference in post-exercise quadriceps twitch force using a bronchodilator intervention vs placebo in 18 COPD patients.

Data from our laboratories, and from others where muscle fatigue was measured from change in stimulated twitch force in COPD patients, suggest that the variance within groups will be 20 times the variance explained by the main effect (that is, a  $\sigma$  ratio 20:1), giving an effect size for AF and MF of  $f=0.23$ . For an  $\alpha$  of 0.05 and strong correlation between repeated measures ( $r=0.80$ ; unpublished data), the actual power is 0.95 with  $n=21$  patients (G\*Power 3.1.5).

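### The 0.95 power stated for activation fatigue (AF) is unsupported: the plan expects a smaller effect than oxygen's but assumes a standardised effect no smaller than oxygen's

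*Combined protocol and SAP*

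**What the plan says.** Section 8 i), Power calculation, describes an unpublished pilot from the investigators' laboratory: 13 COPD patients, paired measurements at isotime, inhaled oxygen as the intervention. It reports a "significant reduction in activation fatigue (AF = 33 Watt reduction", with p=0.03, and a "non-significant increase in muscle fatigue (MF = 9 W increase", with p=0.26. It then says that "the expected difference in PF and AF following bronchodilator therapy are less than for inhaled oxygen".

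The next paragraph gives the planning assumption. Data from the investigators and from studies "where muscle fatigue was measured from change in stimulated twitch force in COPD patients" are said to suggest that "the variance within groups will be 20 times the variance explained by the main effect", "giving an effect size for AF and MF of" f=0.23. With alpha 0.05 and a "strong correlation between repeated measures" of 0.80, it states a power of 0.95 with 21 patients. It gives no watt difference, SD, sidedness or number of measurements for this calculation.

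The Analysis Plan compares AF at isotime on the active drug with AF at intolerance on placebo by a paired t-test, and ties the result to the primary objective.

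**The concern.** The two paragraphs pull in opposite directions. The first expects an AF effect below oxygen's. The second plans on a standardised AF effect at or slightly above the one that the oxygen pilot implies, and nothing between them reconciles the two. The twitch-force studies cannot do so for AF, because by the plan's own description they measure muscle fatigue.

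The 0.95 is the only quantitative justification for 21 patients. A reader who accepts it would take a non-significant AF result as having about a 5% chance of missing a real effect. If the effect is smaller than oxygen's, as the plan expects, that chance is several times larger.

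**Working it through.** **Inputs.** From the Power calculation: f=0.23, r=0.80, alpha 0.05, n=21, stated power 0.95; pilot n=13, AF 33 W, p=0.03. From the Analysis Plan: paired t-test on two conditions. Assumed, because not stated: the planned test and the pilot p-values are two-sided, and the pilot p-values come from paired t-tests.

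**1. Reproducing 0.95.** In a repeated-measures ANOVA with m measurements, the noncentrality is f² × n × m/(1 − r), with m − 1 and (n − 1)(m − 1) degrees of freedom.

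- m=3: 0.0529 × 21 × 3/0.2 = 16.66 on 2 and 40 df; power 0.950. This matches the plan.
- m=2, equivalent to the two-sided paired t-test: 0.0529 × 21 × 2/0.2 = 11.11; power 0.887.
- One-sided paired t-test: power 0.942, close to the stated figure.

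So 0.95 fits three measurements (or, nearly, a one-sided test), not a two-sided paired t-test.

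**2. The plan's effect as a paired standardised difference.** dz = 2f/√(2(1 − r)) = 0.46/√0.4 = 0.727. If f is taken exactly as √(1/20) = 0.224, dz = 0.707.

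**3. The pilot's AF effect on the same scale.** p=0.03 on 12 df gives t=2.461, so dz = 2.461/√13 = 0.682. Rounding of p (0.025 to 0.035) gives 0.71 to 0.66. The 95% CI for dz is about 0.06 to 1.28. The implied SD of paired AF differences is 33/0.682 = 48 W (about 46 to 50 W over the rounding).

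**4. Power of the two-sided paired t-test at n=21** (noncentral t, 20 df, noncentrality dz × √21):

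| AF effect | dz | Power |
|---|---|---|
| Plan's own assumption | 0.727 | 0.887 |
| Equal to oxygen's (33 W) | 0.682 | 0.845 (0.82 to 0.87 over rounding of p) |
| 90% of oxygen's (29.7 W) | 0.614 | 0.76 |
| 75% of oxygen's (24.8 W) | 0.512 | 0.61 |
| 50% of oxygen's (16.5 W) | 0.341 | 0.32 |

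The percentages are assumptions; the plan does not say how much smaller the effect will be.

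**5. Detectable AF difference at n=21.** 80% power needs dz = 0.643, so 0.643 × 48.4 = 31 W. 95% power needs dz = 0.828, so 0.828 × 48.4 = 40 W. Oxygen gave 33 W, so 95% power needs an effect about 21% larger than oxygen's (40/33 = 1.21).

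**The case against.** **The gap between 0.73 and 0.68 is noise.** This stands. With f = √(1/20) and the most favourable rounding of p, the two values meet (0.707 and 0.710), and the pilot interval covers both. A reader might infer that the plan visibly inflated the pilot effect; the figures do not show that. What remains is that the planned effect is no smaller than oxygen's while the plan expects a smaller one.

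**Part of the shortfall is not effect size.** This also stands. Of the drop from 0.95 to 0.845, about 0.06 (0.950 − 0.887) comes from the calculation not matching the planned test, and about 0.04 (0.887 − 0.845) from the effect.

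**A smaller watt difference can still be a large standardised one.** True if paired differences vary less with a bronchodilator. With 33 W or less, dz of 0.727 needs an SD of at most 33/0.727 = 45 W, and 95% power needs at most 33/0.828 = 40 W. The plan states no such SD.

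**The plan admits that power is hard to formalise, and never says that a null AF result would count against the mechanism.** Both are true. The Analysis Plan interprets only a lower AF. The misreading is therefore a risk created by an unqualified 0.95, not something that the plan commits to.

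**Stronger readings that the documents do not support.** A reader might infer from the 9 W pilot result that MF is essentially unpowered. That figure is an isotime contrast, where the Analysis Plan regards similar MF as consistent with its hypothesis. The increase that it hypothesises is at the limit of tolerance, for which the pilot gives nothing. The expectation of a smaller effect than oxygen's also names performance fatigue and AF only, not MF. A reader might also scale AF by the 10% bronchodilator and 22% oxygen figures; these are twitch force and performance fatigue, so their ratio says nothing about AF.

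**Conclusion.** The point holds for AF. In the two-sided paired t-test with 21 patients, power is 0.887 at the plan's own effect, about 0.85 (0.82 to 0.87) if the bronchodilator matches oxygen, and less if, as the plan expects, it does not: about 0.76 to 0.32 over an assumed 90% to 50% of oxygen's effect. At 75%, the chance of missing a real effect is about 39%, not 5%.

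This rests on the pilot p-value being from a two-sided paired t-test. If it was one-sided, the pilot dz falls to about 0.58, power at oxygen's effect is about 0.71, and the discrepancy widens. It also rests on the pilot point estimate, which is imprecise; that is a further reason not to state a single figure of 0.95.

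For MF the conclusion is narrower: the pilot isotime figure does not inform the hypothesised contrast at the limit of tolerance, so the 0.95 needs its own stated basis. It does not follow that the trial must be larger.

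**What to change.** Keep 21 patients. In the Power calculation:

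- Remove the 0.95 for AF. Replace it with the power of the planned paired t-test, sidedness stated, over a stated range of AF effects at or below oxygen's, and with the AF difference detectable at 80% power.
- Compute these from the actual SD of paired AF differences in the pilot data. The back-calculated 48 W (31 W detectable at 80% power, 40 W at 95%) shows what to expect; it is not a reported value and should not be entered as one.
- For MF, name the contrast that the power refers to and the data behind it, or withdraw the figure. Say that the pilot isotime result does not inform the contrast at the limit of tolerance.

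In the Analysis Plan, add that a non-significant AF result will be reported with its 95% CI and not read as absence of effect.

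The cost is one recalculation from pilot data and a change of protocol wording. No patients, visits or tests are added. The stated power becomes less favourable.
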